### **2.3 Exploratory Objective**

We will also examine the impact of IDO2 polymorphisms in depression rates and response to anti-depressants.

### **2.4 Endpoints/Outcome Measures**

Endpoints will include depression, quality of life, survival endpoints, and biomarkers.

#### **Primary:**

The primary outcome measure will be depression rates, based on answers from the QIDS form. Depression is reflected by a score  $\geq 11$  (moderate depression or worse).

#### **Secondary:**

The secondary outcome measures will include:

- Quality of life, as measured by the FACT-Hep total score, and FACT-Hep subscores.
- Measurements of overall survival

#### **Exploratory:**

Exploratory endpoints include:

- genetic biomarkers
- tissue biomarkers of resected specimens
- tissue biomarkers in the plasma or blood
- early PDA recurrence or clinical evidence of disease after resection or radiographic progression in patients who have not yet had surgery (early recurrence is defined as progression of disease within 8 months after the start of systemic chemotherapy)

### **3.0 Study Design**

This trial is a phase II, prospective, randomized, placebo controlled trial, evaluating escitalopram (vs. placebo) in patients with localized pancreatic or periampillary cancer.

### **3.1 Study Characteristics**

Patients may be non-depressed or depressed. Those who are severely depressed according to the Quick Inventory of Depression Survey (QIDS  $\geq 16$  points) will be referred to a psychiatrist for further evaluation and possibly additional therapy, based on clinical judgement. The study will be started at University Hospitals Cleveland Medical Center with the possibility that it can be opened at alternative sites if needed for patient accrual.

At the time of study enrollment, the treating physician must have the intent to treat the patient with 12 weeks of neoadjuvant chemotherapy as standard of care cancer treatment. For this study, patients will be randomized in a 1:1 ratio to receive escitalopram or placebo using a randomization table prepared by the study statistician. This randomization table will be shared by the statistician only with the Investigational Drug Services Pharmacy (IDS) personnel and will detail for all 55 patients/study IDs whether that patient is to receive escitalopram or placebo. Each patient will be

assigned a study number, in sequential order, only after all eligibility criteria have been confirmed by the study coordinator, treating physician (Investigator or Co-investigator) involved in the case, and by a member of the Clinical Trials Unit's Quality Assurance department.

It is possible that burden of disease could influence mood. Therefore, patients will also be stratified according to whether they have resectable disease or locally advanced disease (borderline resectable or unresectable) according to NCCN criteria. A pancreatic surgeon (PI or Co-Investigator) will determine this status using the Tumor Profile Assessment (see Appendix VIII). The Tumor Profile Assessment is to be filled out by the PI or by the Co-investigator prior to randomization.

### **3.2 Number of Subjects**

The clinical trial is powered for 46 patients, including 23 patients in each arm (escitalopram and placebo). However, 55 patients will be enrolled, in order to achieve the desired number due to expected attrition both before and after initiation of therapy or due to removal from study due to reasons noted in Section 6.2.

### **3.3 Replacement of Subjects**

Patients will not be replaced.

### **3.4 Expected Duration of Treatment and Subject Participation**

Patients will be treated with escitalopram or placebo for 12 weeks. An end of treatment visit and assessment will be conducted at Week 13 and another at Week 25. After Week 25, patients will be followed every three months for three years for treatment details and to document disease and survival status.

The typical course of neoadjuvant therapy for resectable or unresectable patients is virtually always  $\geq 12$  weeks. Patients whose cancer progresses during that time will remain on study unless the patient meets criteria for removal from study as noted in Table 7.1 or if the patient becomes unable to swallow oral medications.

The first day of medication will be considered day = zero with respect to the depression (QIDS-SR, PHQ-9) and QOL (FACT-Hep) survey time points (Survival analyses however will be dated back to the date of consent). Surveys will be performed biweekly for 12 weeks. The FACT-Hep will be administered at a slightly less frequent interval (once per month). In the follow-up phase, beginning after Week 25, subjects will be followed for up to 3 years, for recurrence, treatment details, and survival information. Follow-up information will be obtained every 3 months.

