## 11.0 STUDY PARAMETERS AND CALENDAR

### 11.1 Study Parameters

#### 11.1.1 Screening Evaluation:

The following must be completed within 28 days of initiating treatment:

- Informed consent
- Medical history
- Review of current medications
- Physical exam to include head and neck, pulmonary, cardiovascular, gastrointestinal, musculoskeletal, cognitive and cutaneous systems
- Electrocardiogram
- Pregnancy test for patients of child-bearing potential (ie. women who are pre-menopausal or not surgically sterile)
- ECOG

The following must be completed Week 1, Day 1 (clinic visit):

- ECOG performance status
- Blood collection for plasma metabolites
- FIBSER Side effect questionnaire
- QIDS-SR baseline survey for depression
- PHQ-9 Patient Health Questionnaire
- FACT-Hep quality of life survey
- Provide supply of blinded escitalopram/placebo and pill diary to patient
- Explain study procedures including dosing, completion of pill diary and questionnaires
- Toxicity assessment

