### **Survival**

Overall survival will be measured from the date of randomization to date of death or last follow-up, and adjusted for staging. The distribution of survival time will be estimated using the Kaplan-Meier method, and randomization groups will be compared using a stratified log-rank test.

The primary and secondary analyses will be performed on all randomized patients. Patients will be analyzed according to randomization assignment, regardless of the treatment actually received.

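### Overall survival has two time origins: consent in Section 3.4 and randomization in Section 14.2; dating from consent adds time in which no analysed patient can die

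*Combined protocol and SAP*

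**What the plan says.** Section 3.4 (Expected Duration of Treatment and Subject Participation) sets day zero for the depression and quality-of-life surveys at the first day of medication. It then makes an exception in parentheses: "Survival analyses however will be dated back to the date of consent".

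Section 14.2, under Survival, has a different rule: "Overall survival will be measured from the date of randomization to date of death or last follow-up". The same part of the plan specifies Kaplan-Meier estimation, a stratified log-rank test, and the analysis set: "The primary and secondary analyses will be performed on all randomized patients".

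Section 2.4 lists "Measurements of overall survival" as a secondary outcome. No other time-to-death endpoint is named.

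Three places fix the order of consent and randomization:

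- Section 11.1.1 puts informed consent on the screening list, headed "The following must be completed within 28 days of initiating treatment".
- Section 3.1 says a study number is given "only after all eligibility criteria have been confirmed by the study coordinator" and others, and adds: "The Tumor Profile Assessment is to be filled out by the PI or by the Co-investigator prior to randomization".
- Section 5.0 provides for people who consent but are not enrolled.

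**The concern.** Two current sections give different start dates for the same endpoint, and nothing in the documents says which prevails. An analyst could follow either in good faith, and the choice could be made after the data are seen.

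The two origins are not equally good. A person who dies or becomes ineligible between consent and randomization never enters the all-randomized set. If the clock starts at consent, everyone who is analysed has by construction survived the interval up to randomization. That interval adds to survival time but cannot contain a death. Kaplan-Meier curves, medians and landmark survival rates then look slightly better than they should. They are also not comparable with results dated from randomization.

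**Working it through.** The plan states no survival median, event count, hazard ratio or survival power, so there is no figure of its own to reproduce. The check has two parts: whether the contradiction is real, and how large its effect can be.

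**1. Do the two statements concern the same endpoint?**

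- Section 3.4: survival analyses start at consent.
- Section 14.2: overall survival starts at randomization.
- Section 2.4: overall survival is the only survival outcome. The other time-based disease outcome, early recurrence, has its own origin (start of systemic chemotherapy), so Section 3.4 cannot be referring to that.
- Neither sentence belongs to the summary of changes; both are current text.

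The contradiction is real.

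**2. Are consent and randomization different dates?**

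Yes. Eligibility must be confirmed and the Tumor Profile Assessment completed between the two (Section 3.1), and some consented people are expected not to enrol (Section 5.0).

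**3. How long can the gap be?**

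Consent must fall within 28 days before treatment starts (Section 11.1.1), and randomization comes before the first dose. For any patient who starts treatment:

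- 0 ≤ gap ≤ 28 days
- ceiling in months: 28 / 30.44 = 0.92
- mean, if the gap were uniform on 0 to 28 days (assumption): 14 / 30.44 = 0.46 month

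**4. Effect on absolute survival**

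The medians are assumptions, because the documents give none. The 12-month landmark is also an illustration. It uses exponential survival, S(t) = 2^(−t/median), and the full 28-day gap, so that S(12) is read at 12 − 0.92 = 11.08 months.

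| Assumed median (months) | Ceiling as share of median | 12-month survival from randomization | 12-month survival from consent | Difference (percentage points) |
|---|---|---|---|---|
| 12 | 0.92/12 = 7.7% | 2^(−12/12) = 50.0% | 2^(−11.08/12) = 52.7% | 2.7 |
| 18 | 0.92/18 = 5.1% | 2^(−12/18) = 63.0% | 2^(−11.08/18) = 65.3% | 2.3 |
| 24 | 0.92/24 = 3.8% | 2^(−12/24) = 70.7% | 2^(−11.08/24) = 72.6% | 1.9 |

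These are upper limits; shorter gaps give proportionately smaller shifts.

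**5. Effect on the comparison between arms**

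This was checked by simulation, with each simulated trial analysed from both origins.

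- From the documents: 55 randomized 1:1 (27 and 28), and follow-up for three years after Week 25, taken as 42 months.
- Assumed: exponential survival, control medians of 12, 18 and 24 months, hazard ratios of 1.0 and 0.7, and a gap uniform on 0 to 28 days. The test was a two-sided 5% unstratified log-rank test, with 4,000 runs per case.

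| Control median (months) | Hazard ratio | Rejection rate, from randomization | Rejection rate, from consent |
|---|---|---|---|
| 12 | 1.0 | 6.1% | 6.2% |
| 18 | 1.0 | 5.3% | 5.3% |
| 24 | 1.0 | 5.2% | 5.4% |
| 12 | 0.7 | 24.3% | 24.1% |
| 18 | 0.7 | 21.1% | 21.0% |
| 24 | 0.7 | 18.9% | 18.9% |

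The mean estimated log hazard ratio differed by less than 0.001 in every case. With a fixed 28-day gap for everyone (18-month median, 1,000 runs per hazard ratio) the log-rank results were identical. That is expected: adding a constant to every time leaves the order of events unchanged.

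**The case against.** The other side accepts that the two sections disagree and argues that it hardly matters.

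- **Guaranteed survival time usually signals a biased comparison, and here it does not.** The interval precedes allocation and cannot depend on arm, and patients are analysed as randomized. This stands. Consent dating distorts the absolute estimates; it does not materially bias the treatment effect.
- **The 28 days limit consent to first dose, and the documents never give the gap from consent to randomization.** This also stands. The figure is a ceiling, many gaps will be shorter, and it does not strictly bind a randomized patient who never starts treatment. The size should be read as a range from 0 to 28 days.
- **A statistician would probably follow Section 14.2.** That section names the origin, event, estimator and test, while the conflicting words are a parenthesis about survey timing. This is likely, but the documents set no order of precedence. The parenthesis is also worded as a deliberate exception for survival, so it cannot be dismissed as loose phrasing.
- **Overall survival is secondary, and the sample size rests only on depression at 12 weeks.** This is true and limits the importance of the point. It does not tell the analyst which date to use.

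**Conclusion.** The concern holds. Sections 3.4 and 14.2 give incompatible start dates for overall survival, and the one in Section 3.4 does not fit an analysis set defined by randomization. Following it would add 0 to at most 28 days (0.92 month) of guaranteed survival to each treated patient's time. It would raise medians and landmark rates slightly and leave the between-arm test practically unchanged.

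The contradiction and the direction of the shift rest on the text alone. The 28-day ceiling comes from the screening window and assumes that window is kept. The percentages of the median, the landmark differences and the simulated rejection rates rest on the assumed medians, hazard ratios and exponential survival. The simulation also used an unstratified test where the plan specifies a stratified one.

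This is a minor point: a secondary endpoint, and a small shift that is the same in expectation in both arms.

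**What to change.** Delete the parenthesis in Section 3.4, or reword it so that survival is measured from randomization as in Section 14.2. Record the randomization date explicitly as time zero for overall survival in the analysis dataset, and make the correction before any survival data are analysed.

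The cost is one phrase in the next amendment. Visits, data collection, sample size and patient management are unaffected.

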## **4.0 Subject Selection**

Each of the criteria in the sections that follow must be met in order for a subject to be considered eligible for this study. Use the eligibility criteria to confirm a subject's eligibility.

**Subject's Name** \_\_\_\_\_

**Medical Record #** \_\_\_\_\_

#### **4.1 Inclusion Criteria**

Subjects must meet all of the following inclusion criteria to be eligible for enrollment:

- \_\_\_ 4.1.1 Patients must have histologically or cytologically confirmed localized or locally advanced pancreatic ductal adenocarcinoma or other periampullary adenocarcinoma (bile duct, duodenal, ampullary)
- \_\_\_ 4.1.2 Patients must not currently be on an antidepressant, anti-anxiety, anti-bipolar, or anti-psychotic medicine
- \_\_\_ 4.1.3 Aged 18-80 years.
- \_\_\_ 4.1.4 ECOG PS score of 0-2
- \_\_\_ 4.1.5 Planned to have at least 12 weeks of neoadjuvant chemotherapy as standard of care cancer treatment
- \_\_\_ 4.1.6 No diagnosis of bipolar disease
- \_\_\_ 4.1.7 Willing to comply with all study procedures and be available for the duration of the study
- \_\_\_ 4.1.8 Patient must be mentally competent and must have the ability to understand and the willingness to sign a written informed consent document
- \_\_\_ 4.1.9 Patients must be able to speak English

#### **4.2 Exclusion Criteria**

The presence of any of the following will exclude a subject from study enrollment.

- \_\_\_ 4.2.1 Patients under the age of 18 or over age of 80

- 4.2.2 Metastatic pancreatic or other periamppullary cancer
- 4.2.3 Resection of pancreatic cancer within the past year prior to study enrollment or planned surgery within the next 12 weeks
- 4.2.4 Currently on an antidepressant, anti-anxiety, anti-bipolar or anti-psychotic medicine. Patients who have taken MAOI inhibitors within the past 6 months are excluded.
- 4.2.5 Patients with a diagnosis of bipolar disease
- 4.2.6 Patients with a history of seizure disorder
- 4.2.7 Patients with a recent medical history of myocardial infarction or unstable heart disease
- 4.2.8 Patients with a history of QTc prolongation or torsade de points, a baseline QTc interval of > 500ms, a history of drug-induced QTc prolongation or congenital long QT syndrome
- 4.2.9 Patients with Child-Pugh score of B or C
- 4.2.10 Patients with moderate to severe renal disease with a GFR < 45.
- 4.2.11 Patients who cannot ingest oral medication
- 4.2.12 Patients with any history of mania
- 4.2.13 Patients with known allergy to escitalopram
- 4.2.14 Patients who are pregnant or lactating
- 4.2.15 Patients who do not speak English

### **4.3 Inclusion of Women and Minorities**

Both men and women and members of all races and ethnic groups are eligible for participation in this trial. Children (under 18) will be excluded. Note that escitalopram is safe and effective in the elderly .

### **5.0 Registration**

All subjects who have been consented are to be registered in the OnCore™ Database. For those subjects who are consented, but not enrolled, the reason for exclusion must be recorded.

All subjects will be registered through University Hospitals Cleveland Medical Center and will be provided a study number by contacting the study coordinator listed on the cover page.

## **6.0 Treatment Plan**

### **6.1 Treatment Regimen Overview**

This interventional trial involves the administration of a safe and well-tolerated oral antidepressant. Patients will take escitalopram or placebo, at the standard dose, with a ramp-up and ramp-down interval, as previously described in a similar trial in head and neck cancer .

The schedule is as follows:

2 weeks: 10 mg/day (1 capsule)

8 weeks: 20 mg/day (2 capsules)

2 weeks: 10 mg/day (1 capsule)

Patients will come to the clinic on Day 1 and will be given a pill diary and enough blinded escitalopram/placebo for the first 2 weeks of the study. The patient will be taught how/when to take the pills and how to complete the pill diary. The patients will be given pill bottles for Weeks 1-2. Patients will take their first dose of escitalopram/placebo and have blood drawn for serum metabolites at this visit (prior to dosing). The QIDS-SR depression survey, PHQ-9, FACT-Hep QOL and FIBSER Side Effect Questionnaires (see Appendices IV, V, VI and VII) will be completed. A member of the study staff will give the questionnaires to the patient to complete in a private area. The study staff member will remain with the patient during completion of the questionnaires to assist, if necessary, and to ensure that the patient is answering all questions on their own.

There will be study-related clinic visits scheduled for Days 15 and 71. On Day 15, patients will be given pill bottles for Weeks 3-10. On Day 71, patients will be given pill bottles for Weeks 11-12. The Week 11-12 pill diary along with any unused pills will be collected at the end of treatment clinic visit (Week 13, Day 85). All other visits will be conducted via phone call from the study staff every two weeks beginning on Day 8. Phone visits will be conducted on Days 8, 22, 36, 50, 64 and 78 (+/- 7 days). However, if a patient's scheduled chemotherapy-related visit, clinic visit or hospital visit for any other reason happens to fall on (or within the 7 day window of) a planned study visit, the visit may be conducted in person with study staff. During these visits (phone or in-person), the study staff will perform a toxicity assessment and ask questions to determine if the patient is being compliant with taking the pills and completing the pill diary. The study staff member will verbally conduct the QIDS-SR, PHQ-9, and FIBSER with the patient and record the patient's answers and the FACT-Hep will be given directly to the patient to complete (if not done over the phone). The FACT-Hep will be performed monthly on Days 1, 22, 50 78, and 85.

#### Unblinding Procedures:

- Patients will be unblinded if study drug is discontinued for the Adverse Events of Special Interest (hemorrhage, suicidal ideation and mania) as described in Table 7.1.
- Patients will be unblinded if study drug is discontinued due to Grade 4 hyponatremia as described in Table 7.1.

- Patients will be unblinded if they meet the criteria for removal from study as defined in Section 6.2.
- Patients will be unblinded at the time of their Day 85 (Week 13) end of treatment visit.

Patients will be unblinded by IDS staff as outlined in the Unblinding Manual. Patients who are unblinded before they complete all study visits will be asked to continue to have study-related phone calls with study staff and complete all study-related questionnaires. Patients who are unblinded prior to the end of treatment visit and undergo tumor resection will be required to have the research tissue sample and post-surgery research blood samples taken.

An assessment of depression will be made by the treating physician. Based on the assessment, patients who received escitalopram may be given the option of continuing the medication either under the supervision of their medical oncologist or primary care provider. If this occurs, the patient will obtain escitalopram from commercial supply at the dose prescribed by the patient's medical oncologist, primary care physician or other provider.

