## **6.2 Criteria for Removal from Study**

### **Withdrawal Visit/Discontinuation of Therapy**

In the absence of treatment delays due to adverse events, treatment may continue for 12 weeks or until one of the following criteria applies:

- Patient misses more than four consecutive weeks of escitalopram.
- Intercurrent illness that prevents further administration of treatment or patient inability to swallow escitalopram/placebo capsules,
- The investigator considers it, for safety reasons, to be in the best interest of the patient.
- Unacceptable adverse event(s):

-NCI CTCAE version 5.0 Grade 2 or higher hemorrhage that occurs within the first four weeks of treatment  
-NCI CTCAE version 5.0 Grade 4 suicidal ideation  
-NCI CTCAE version 5.0 Grade 3 or higher mania  
-NCI CTCAE version 5.0 Grade 4 hyponatremia

Patients who experience severe depression will be referred to a psychiatrist. They will also continue, if agreeable, on the study and with scheduled surveys according to the defined schedule (QIDS, PHQ-9, FACT-Hep, FIBSER).

Patients will be withdrawn if they are deemed at high risk for suicide or if they wish to voluntarily withdraw from the study.

- Patient decision to withdraw from treatment (partial consent) or from the study (full consent),
- Pregnancy during the course of the study
- Death

- The Principal Investigator and/or the Case Comprehensive Cancer Center Data Safety Toxicity Committee (DSTC) reserve the right to temporarily suspend or prematurely discontinue this study if unacceptable study-related risks are identified. The date and reason for discontinuation must be documented. Every effort should be made to complete the appropriate assessments.

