## **Handling of Participant Withdrawals and Participant Discontinuation of Study Intervention**

Patients who withdraw from treatment will have an end of study visit as described in Section 6.3. They will continue to be followed with surveys at the scheduled intervals and for cancer-specific outcomes, unless patients refuse this follow-up by withdrawal of consent.

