### **7.0 Dose Delays/Dose Modifications**

The starting dose will be one pill (10mg of escitalopram/placebo) during Weeks 1 and 2 followed by two pills daily (20mg of escitalopram/placebo) during Weeks 3-10 then one pill (10mg of escitalopram/placebo) during Weeks 11-12. Drug toxicities will be assessed based upon responses to questionnaires and from entries on pill diaries every two weeks by the clinical staff during the scheduled phone calls or in-person visits. There will be no dose reductions. Drug will be discontinued for the Adverse Events of Special Interest (hemorrhage, suicidal ideation and mania)

and for Grade 4 hyponatremia as described in Table 7.1. Drug may also be discontinued, at the discretion of the treating physician, for other adverse events determined by the PI to be related to escitalopram/placebo. If the event takes place in the first four weeks of starting treatment, the patient will be removed from study and will not be followed.

Patients who discontinue drug for any reason will continue to complete all questionnaires as outlined on the Study Calendar. The study team will make every effort to ensure that patients stay on schedule.

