### **9.1 Investigational Agents**

**9.1.1 Name of Agent** Escitalopram

Other Names: Lexapro

**Product description:** Escitalopram and placebo will be supplied as 10 mg capsules

**Formulation, Packaging and Labeling:** All aspects of drug and placebo manufacturing, preparation, packaging, and labeling will be managed by Buderer Drug Co. Escitalopram will be supplied as a 10mg oblong white tablet, commercially manufactured pharmaceutical by Aurobindo, supplied by Buderer Drug, over-encapsulation in a #1 dark blue capsule. Twenty (20) capsules placed into a labeled child resistant prescription vial. Eight (8) bottles will be supplied for each patient. Placebo is a white capsule containing microcrystalline cellulose, compounded (to match the weight of the escitalopram 10mg tablet) over-encapsulation into a #1 dark blue capsule. Twenty capsules placed into a labeled child resistant prescription vial. Eight (8) bottles will be

supplied for each patient. A batch will be prepared every 180 days or sooner as required. Bottles will be labeled with the patient's study number, blinded ID (B or D) and drug storage information.

**Storage requirements and stability:** Stability will be for six months duration, and stable at room temperature 15°-30°C (59°-86°F).

**Route of administration:** There will be no mixing or added preparation by pharmacists, technicians or nurses once the finished clinical supply is received from Budrer. Patients will take escitalopram or placebo at the standard dose, with a ramp up and ramp down interval as follows:

2 weeks: 10 mg (1 capsule)

8 weeks: 20 mg (2 capsules)

2 weeks: 10 mg (1 capsule)

**Drug Procurement:** Escitalopram and placebo for this study will be obtained from Buderer Drug Co.

**Drug Accountability:** Orders will be placed by study staff and product shipped by Buderer and stored at University Hospital's Investigational Drug Services Pharmacy at room temperature for the duration of the trial. Patients will be given one bottle of escitalopram/placebo upon study initiation for the first two weeks on study. At Day 15 patients will be given six bottles for the next eight weeks and at Day 71 patients will be given one bottle for the remainder of the study.

Investigational Drug Services Pharmacy is responsible for maintaining accurate dispensing records of the study drug.

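### Section 6.2 removals that do not in themselves require knowing the arm still open the code, and these patients' later self-reported QIDS-SR answers go into the 12-week primary comparison

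*Combined protocol and SAP*

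**What the plan says.** Section 6.1 (Unblinding Procedures) gives separate triggers for the adverse events of special interest and for Grade 4 hyponatremia. It then adds a general one: "Patients will be unblinded if they meet the criteria for removal from study as defined in Section 6.2". Routine unblinding takes place at the Day 85 visit.

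Section 6.2 lists safety events, but also "Patient misses more than four consecutive weeks of escitalopram", "Intercurrent illness that prevents further administration of treatment or patient inability to swallow escitalopram/placebo capsules", and the patient's own choice to leave treatment while staying in the study.

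Patients unblinded early remain in data collection. Section 6.1 says they "will be asked to continue to have study-related phone calls with study staff and complete all study-related questionnaires". For those who withdraw from treatment, the part of Section 6.2 on handling withdrawals says "They will continue to be followed with surveys at the scheduled intervals and for cancer-specific outcomes", unless consent is withdrawn. Section 7.0 says "Patients who discontinue drug for any reason will continue to complete all questionnaires as outlined on the Study Calendar".

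Under Section 6.1, study staff read out the QIDS-SR at phone visits and record the answers. Section 14.2 makes depression by QIDS at 12 weeks the primary endpoint, models the repeated QIDS-SR measurements through 12 weeks, and analyses all randomized patients as assigned.

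**The concern.** The primary endpoint is self-reported mood, the kind of outcome for which blinding matters most. A patient told that the capsules were placebo, or that they were escitalopram, may answer later questionnaires differently. Staff who know the arm may also put the questions or record the replies differently. There is a further route: Section 6.1 allows patients found to have received escitalopram to continue it from commercial supply, so care itself can diverge by known arm before week 12.

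Because the safety triggers already have their own entries in Section 6.1, the general trigger mainly adds removals where opening the code may serve no immediate need. At stake is the credibility of a one-sided 10% test with 23 patients per arm, where a few altered answers matter. Section 14.2 plans imputation for missing outcomes but has no analysis for answers given after an early code break.

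**Working it through.** **Following one patient through the plan.** Take a patient who decides to stop the capsules in week 5 but agrees to stay in the study.

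1. Section 6.2: this is a removal criterion.
2. Section 6.1: the patient is therefore unblinded, before the 12-week assessment.
3. Sections 6.1, 6.2 and 7.0: the questionnaires continue.
4. Section 14.2: the patient is analysed as randomized, so the 12-week QIDS-SR counts.

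No section withholds the assignment until that score is in. The chain does not run for patients who die or withdraw consent fully, since they give no 12-week score.

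Two sections leave the chain unclear for some others. Section 7.0 says that patients whose event falls in the first four weeks will not be followed. Section 14.3 calls patients with under 65% compliance after four weeks, and those stopping for a serious adverse event in that period, not evaluable. Neither fits Sections 6.1 and 14.2.

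**The plan's own figures.** Section 14.3: 23 per arm, 40% versus 13.8%, one-sided alpha 0.10, 80% power.
- Unpooled normal approximation: SE = sqrt(0.40 x 0.60/23 + 0.138 x 0.862/23) = 0.1249. Then 0.262/0.1249 - 1.2816 = 0.816, giving power of 79.3%.
- Exact enumeration of the pooled score test: 80.1%.
- Randomized number: 46/0.85 = 54.1, rounded up to 55.

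The design figures reproduce.

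**Illustration of size.** From the plan: 23 per arm, the 40% control rate and one-sided alpha 0.10. Assumed, and not in the documents:
- The true rate is 40% in both arms.
- A share u of each arm is unblinded early and still answers.
- Knowing the arm shifts the chance of QIDS-SR depression by +d on placebo and -d on escitalopram.

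Formulas: bias in the risk difference = 2 x u x d. SE = sqrt(2 x 0.24/23) = 0.1445. Type I error = P(Z > 1.2816 - bias/SE).

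| u | Patients per arm | d | Bias | Type I error |
|---|---|---|---|---|
| 5% | 0.05 x 23 = 1.15 | 0.05 | 0.005 | 0.106 |
| 5% | 1.15 | 0.15 | 0.015 | 0.119 |
| 15% | 0.15 x 23 = 3.45 | 0.05 | 0.015 | 0.119 |
| 15% | 3.45 | 0.15 | 0.045 | 0.166 |

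This is a plain two-proportion approximation, not the baseline-adjusted modified Poisson GEE of Section 14.2. It shows the order of magnitude only.

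**The case against.** **Size.** A reader might take the 15% attrition allowance in Section 14.3 as the share unblinded early. The documents do not support that. The allowance exists so that 46 of 55 patients remain at 12 weeks, so it describes patients without usable 12-week data, whereas the concern is with unblinded patients who do answer. The number of these appears nowhere. The 15% row above is an arbitrary upper illustration, and at 5% the effect is small.

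**Direction.** A reader might infer that the bias must favour the drug. That is the most plausible direction, but it is not shown. A patient told placebo could seek open-label treatment, and Sections 6.3 and 7.0 provide referral of patients with high scores. Either could lower the placebo rate.

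**Scope.** A reader might say that every Section 6.2 removal contaminates the outcome. Death and full withdrawal of consent do not, and the Section 7.0 and 14.3 wording leaves others unsettled.

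**Letter codes.** Section 9.1 labels bottles with a "blinded ID (B or D) and drug storage information". A reader might infer that one early break reveals the arm of everyone else. The documents do not say that each letter is one arm. If it were, routine Day 85 unblinding would expose the mapping once the first patient finished, so the early-removal rule would not be the main cause and the change proposed here would not cure it.

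**Need for the arm.** Knowing the arm supports the decision in Section 6.1 about continuing escitalopram. This stands, and the fix must leave room for it. The Unblinding Manual, which is not supplied, may limit who else is told, but Section 6.1 says that patients themselves are unblinded.

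**Conclusion.** The weakness is real but limited. As written, the plan opens the code for removals that do not in themselves require it, keeps asking those patients for the self-reported primary outcome, and analyses the answers with no protection or sensitivity analysis. This follows from the text and does not depend on the illustrated figures.

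The size is unknown. On the stated assumptions, the nominal 10% one-sided error becomes 10.6-11.9% with 5% of patients unblinded and still answering, and 12-17% with 15%. Both the share and the shift are assumed. The sponsor should change the rule because the remedy is cheap and the outcome is sensitive to knowledge of the arm, not because a particular bias has been demonstrated.

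**What to change.** - Leave code breaks as they are wherever the investigator needs the arm for patient safety or care.
- For other Section 6.2 removals, hold the code until the patient's 12-week QIDS-SR, PHQ-9 and FACT-Hep are complete.
- Record the date and reason of every early code break.
- Add a sensitivity analysis to Section 14.2 that sets aside questionnaires answered after an early break. State its limit: early unblinding coincides with stopping the drug, so the analysis cannot separate the two effects.
- Reconcile Section 7.0 (early events not followed) and Section 14.3 (not evaluable) with Sections 6.1 and 14.2, so that it is clear whose scores after removal count.

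The cost is wording in the protocol and Unblinding Manual, a short log and one extra analysis. The downside falls on some patients who stop early. They learn their arm later, by up to about 12 weeks (Day 1 to Day 85 is 84 days), which also delays the Section 6.1 option of continuing escitalopram unless the arm is needed for care.
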